3.1 Description of the Study

This is an open-label, nonrandomized, Phase 1/Phase 2 study to determine the safety and tolerability, define the MTD or PAD, and to assess the preliminary efficacy of NC762 in subjects

with advanced or metastatic solid tumors. Subjects will receive NC762 on Day 1 of each cycle. Phase 1 of the study will begin with 14-day cycles; however, alternate dose administration schedules may also be explored depending on PK, PD, biomarker, safety results, and feedback from investigators. The study will be conducted in 2 parts:

- Phase 1 – Dose Escalation (Phase 1a) and Safety Expansion (Phase 1b) will determine the MTD and/or the PAD, defined as a dose that provides a maximal biochemical effect, or an increase in biomarkers of immune activity. It will also define the optimal dose administration schedule and the maximum number of tolerated doses (MNTD).
- Phase 2 – Dose Expansion will evaluate the recommended dose and administration schedule determined in Phase 1 in subjects with advanced or metastatic non-small cell lung (squamous cell), hepatocellular carcinoma, HER2+ breast, and ovarian cancer, or other tumor type as identified with emerging data.

Figure 1: Study Design

RR: Response Rate (ORR) per RECIST v1.1

3.1.1 Phase 1

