3.1.1.1 Phase 1a - Dose Escalation

In Phase 1a, subjects with advanced or metastatic solid tumors who progressed after treatment with available therapies that are known to confer clinical benefit, who are intolerant to treatment, or refuse standard treatment will be enrolled. A 3 + 3 design will be utilized to determine the MTD or PAD of NC762.

A minimum of 3 evaluable subjects will be enrolled in each cohort beginning with Cohort 1 (0.5 mg/kg; starting dose). The first 3 evaluable subjects within a cohort will be observed for a DLT observation period of 28 days before the next cohort begins enrollment. Only one subject can be dosed on the first day of dosing for each cohort (additional subjects can begin dosing in ≥ 48 hours). The dose will be escalated if 0 of the first 3 evaluable subjects enrolled has a DLT. If 1 of

the first 3 evaluable subjects enrolled has a DLT, then the cohort will be expanded to include 3 additional evaluable subjects, and if no DLT occurs in the additional 3 subjects, then the dose will be escalated. If a DLT occurs in one-third or more of the expanded cohort, then the MTD will be deemed to be exceeded and the previous dose level will be considered the MTD. Intermediate dose levels below the MTD may be explored pending safety review.

If only 3 subjects were treated at the MTD or PAD, then a minimum of 3 additional evaluable subjects will be enrolled at this dose before it is administered in Phase 2 of the study.

If starting dose exceeds the MTD, the sponsor and investigators will consider dosing NC762 at a lower dose, and/or investigate 0.5 mg/kg at alternate dose schedules, based on available safety, PK, PD, and biomarker data. If an alternate schedule is determined to be safe, re-escalation of NC762 will proceed according to Table 2.

Throughout the treatment period, if > 33% of subjects (a minimum of 6 subjects) experience a \geq Grade 3 toxicity related to study drug after completing \geq 4 cycles, then dose administration will be stopped, and the MNTD will be determined in conjunction with the investigators and sponsor based on all available safety data.

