Additional subjects will be enrolled in a cohort to achieve the minimum of 3 evaluable subjects. Subjects who drop out for reasons other than a DLT (e.g., events clearly associated with the underlying disease, disease progression, concomitant medication, or comorbidity) during the 28-day DLT observation period will be considered non-evaluable and will be replaced. Dose modifications should not be made during the DLT observation period without discussion with the medical monitor. Intrasubject dose escalation is not permitted; however, once the RP2D and schedule has been determined, ongoing subjects in Phase 1 may be permitted to escalate to the RP2D only with approval of the medical monitor assuming the subject has not experienced \geq Grade 3 toxicity in previous treatment cycles. The cohorts and dose levels are shown in Table 2.

Table 2: NC762 Dose Levels and Cohorts

Cohort	Dose of NC762
1 (Starting dose)	0.5 mg/kg
2	1.0 mg/kg
3	5.0 mg/kg
4	10 mg/kg
5	20 mg/kg

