
• \geq Grade 2 ocular irAEs• Grade 3 irAEs that do not improve to baseline or at least Grade 1 in < 5 days with appropriate care or with corticosteroid therapy• Grade 4 irAEs regardless of duration.

General

- Inability to receive the planned number of doses within the 28-day DLT period due to toxicity, regardless of grade, will be considered a DLT.
- Combined elevations in serum ALT >3 times the upper limit of normal (ULN) **and** bilirubin >2 ULN in the absence of alkaline phosphatase (ALP) elevation (<2 ULN)
 - Abnormal liver function tests as indicated by the criteria above will be considered a DLT if no other reason can be found to explain the combination of increased liver markers such as viral hepatitis A, B, or C; preexisting or acute liver disease; or another drug capable of causing the observed injury.
- Any death not clearly due to the underlying disease or extraneous causes.

MTD

- In Phase 1 of the study, the MTD will be defined as 1 dose level below that at which \geq one-third of subjects in a cohort have DLTs.
- In Phase 2 of the study, toxicities will continue to be monitored. If the cumulative incidence of DLTs occurs in > 33% of subjects after 6 subjects have been observed for at least 28 days, then further enrollment may be interrupted, and the investigators and sponsor will meet and reassess the MTD. All AEs, regardless of the time of occurrence on study, may be considered in determining the appropriate dose, schedule, and MNTD.

MNTD

- Throughout the treatment period, if > 33% of subjects (minimum of 6 subjects) experience a \geq Grade 3 toxicity related to study drug after completing \geq 4 cycles, then dose administration will be stopped, and the MNTD will be determined in conjunction with the investigators and sponsor based on all available safety data.

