5.4.6 Criteria and Procedures for Dose Interruptions and Adjustments of Study Drug

Treatment with study drug may be delayed allowing for resolution of toxicity. Subjects may resume treatment if no medical condition or other circumstance exists that, in the opinion of the investigator, would make the subject unsuitable for further participation in the study. For toxicities that occur outside of the 28-day DLT period, the treating investigator should contact the medical monitor to discuss the case of any subject whose treatment has been delayed for more than 4 weeks (28 days). **Note:** Patients who have >28-day treatment delay must discontinue from further treatment.

Instructions for dose modifications and interruptions are outlined in Table 4. Individual decisions regarding dose interruptions and reductions should be made using appropriate clinical judgment in consultation with the medical monitor, considering relatedness of the AE to the study drug and the subject's underlying condition. Adverse events that have a clear alternative explanation, or transient (\leq 72 hours) abnormal laboratory values without associated clinically significant signs or symptoms may be exempt from dose-reduction rules. Dose interruptions/delays are permitted in the case of medical/surgical events or logistical reasons not related to study therapy (e.g., elective surgery, unrelated medical events, subject vacation, and/or holidays). Subjects should be placed back on study therapy within 4 weeks (28 days) of the scheduled interruption/delay. The reason for interruption/delay should be documented in the subject's study record.

Table 4: Rules for Interruption and Restarting of Study Drug

NCI CTCAE v5.0 Grade/Severity	Timing for Restarting Treatment	Dose Level for Restarting Treatment	Treatment Discontinuation
1-2 (mild-moderate)	Continue treatment at the discretion of the investigator.	N/A	N/A
3 (severe)	Toxicity resolves to Grade 0-1.	Reduce by 1 dose level. ^a	Toxicity does not resolve within 4 weeks (28 days) of last dose, except by approval of the medical monitor. or Second occurrence of previously resolved Grade 3 AE.
4 (life-threatening)	Permanently discontinue.	N/A	Permanently discontinue.

Note: Permanently discontinue for any severe or Grade 3 AE that recurs or any life-threatening event.

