9.2 Selection of Sample Size

A maximum of 170 eligible subjects in Phase 1 and Phase 2 (50 + 120) will be included in this study.

9.2.1 Sample Size for Phase 1

The primary objective of the dose escalation part in Phase 1 of the study (Phase 1a) is to determine the MTD or PAD of NC762. A 3 + 3 study design will be used for dose escalation. A maximum of 5 dose levels will be tested. Therefore, a maximum of 30 subjects, who are evaluable for DLTs, will be included in the dose escalation phase. Subjects evaluable for DLTs are defined as the subjects who take a full dose of NC762 and then are followed up for 28 days for assessment of DLTs. Any subjects who do not meet the criteria will be replaced.

Phase 1 of the study may also include safety expansion cohorts (Phase 1b) evaluating doses and schedules equivalent to or lower than the highest dose levels determined to be safe and/or doses determined to be pharmacologically active. Each safety expansion cohort will enroll up to an additional 10 evaluable subjects (total of 20 subjects in the Phase 1b). If < 3 of 10 evaluable subjects experience a DLT, the cohort will be deemed safe. If more than 1 safety expansion cohort is deemed safe, then the RP2D will be determined in conjunction with the investigators and sponsor based on all available safety, PK, PD, and biomarker results.

9.2.2 Sample Size for Phase 2

Phase 2 of the study will further evaluate the safety, tolerability, preliminary efficacy, PK, and pharmacologic activity of the recommended dose of NC762. The sample size for each tumor type will be guided by the Simon 2-stage design (Simon, 1989). Let 5% be a clinically insignificant response rate for all tumor types. During Stage 1, 12 subjects will be enrolled; if no responses are observed, then the cohort will be discontinued. If at least 1 response is observed, then 12 additional subjects will be enrolled (Stage 2), for a maximum of 24 subjects per tumor type in Phase 2. The detailed calculation is based on a 1-sided Type I error of 0.05 and power of 80% to detect a 25% response rate for each of the tumor types.

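### A subject whose second dose slips past Day 28 for a non-toxicity reason still counts as DLT-free, which tilts the 3+3 and Phase 1b decisions toward safe

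*Combined protocol and SAP*

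**What the plan says.** Section 9.2.1 defines the denominator of the escalation decision: "Subjects evaluable for DLTs are defined as the subjects who take a full dose of NC762 and then are followed up for 28 days". It adds: "Any subjects who do not meet the criteria will be replaced". No minimum number of doses beyond the first is stated.

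Section 3.1 sets the schedule: "Phase 1 of the study will begin with 14-day cycles", and "Subjects will receive NC762 on Day 1 of each cycle". Section 3.1.1.1 has the first three evaluable subjects "observed for a DLT observation period of 28 days before the next cohort begins enrollment".

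Three provisions deal with incomplete dosing in the window:
- Table 3 (section 5.4.2) counts as a DLT, at any grade: "Inability to receive the planned number of doses within the 28-day DLT period due to toxicity".
- Section 3.1.1.1 and the synopsis treat as non-evaluable, and replace: "Subjects who drop out for reasons other than a DLT".
- Section 3.3.2 says that a Phase 1 subject who withdraws from treatment before the DLT period ends, for a reason other than a DLT, may be replaced.

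Section 5.4.6 covers the subject who stays on study: "Dose interruptions/delays are permitted in the case of medical/surgical events or logistical reasons not related to study therapy". Its examples include elective surgery, vacation and holidays. It expects a return to treatment within 28 days and makes no exception for the DLT window.

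**The concern.** The DLT definition refers to the number of doses planned for the window; the evaluability definition does not. Take a subject dosed on Day 1, away on Day 15 and dosed again on Day 29. There is no toxicity, no drop-out and no withdrawal. The subject meets section 9.2.1 as written and enters the 3+3 count as a subject without a DLT, after half the planned doses.

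The MTD of a repeated regimen is a primary objective, and this is a first-in-human study decided on three or six subjects per level. If a second dose adds any DLT risk, counting one-dose subjects as DLT-free moves the observed rate in one direction only, down. The Phase 1b rule, under which a cohort is deemed safe with fewer than 3 DLTs in 10 evaluable subjects, has no evaluability definition of its own, so the same gap carries over.

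**Working it through.** **The plan's own figure.** Five dose levels × 6 subjects = 30, the stated Phase 1a maximum of DLT-evaluable subjects. It reproduces.

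**Doses in the window.** With 14-day cycles dosed on Day 1, doses fall on Days 1, 15 and 29. Two lie within 28 days.

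**The open route.** Dose 2 leaves the window when it moves from Day 15 to Day 29 or later, a delay of at least 29 − 15 = 14 days. Section 5.4.6 allows up to 28 days, that is up to Day 43. Non-toxicity delays of 14 to 28 days in a subject who remains on study are therefore permitted, and nothing removes that subject from the evaluable set.

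**Effect on the 3+3 decision.** The documents give no one-dose DLT rate. Assume equal, independent risk per dose. With true two-dose rate p, the one-dose rate is h = 1 − √(1 − p). The rule in section 3.1.1.1 gives

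P(escalate) = P(0 of 3) + P(1 of 3) × P(0 of the next 3).

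At p = 0.30, h = 1 − √0.70 = 0.163:
- All subjects receive both doses: 0.343 + 0.441 × 0.343 = 0.494.
- One of the first three receives one dose: P(0 of 3) = 0.837 × 0.49 = 0.410; P(1 of 3) = 0.163 × 0.49 + 0.837 × 2 × 0.3 × 0.7 = 0.431; total 0.410 + 0.431 × 0.343 = 0.558.
- Two of the first three receive one dose: 0.628.

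| True two-dose rate | One-dose rate | All fully dosed | One of first three on one dose | Rise (points) |
|---|---|---|---|---|
| 25% | 0.134 | 0.600 | 0.656 | 5.6 |
| 30% | 0.163 | 0.494 | 0.558 | 6.4 |
| 33% | 0.184 | 0.428 | 0.495 | 6.7 |
| 40% | 0.225 | 0.309 | 0.377 | 6.8 |
| 50% | 0.293 | 0.172 | 0.230 | 5.8 |

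**Sensitivity to the per-dose assumption.** At a 33% rate with one such subject, P(escalate) is 0.465 if one dose carries 75% of the two-dose risk, and 0.576 if it carries none, against 0.428 when all are fully dosed.

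**Weighting by frequency.** The documents give no frequency either. Let each subject have chance m of missing dose 2 this way; the average DLT rate is then (1 − m)p + mh. At p = 0.30:
- m = 5%: rate 0.293, P(escalate) 0.508, a rise of 1.4 points.
- m = 20%: rate 0.273, P(escalate) 0.551, a rise of 5.7 points.

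At 33% the same range of m gives 0.443 to 0.487 against 0.428. The chance that a three-subject cohort contains at least one such subject is 1 − 0.95³ = 14% at m = 5% and 1 − 0.90³ = 27% at m = 10%.

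**Phase 1b.** With nine fully dosed subjects and one on a single dose, P(deemed safe) = P(≤ 2 of 9)(1 − h) + P(≤ 1 of 9)h. At a 33% rate this is 0.334, against 0.299 with ten fully dosed. At 50% it is 0.069 against 0.055.

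**The case against.** The strongest reply is that the gap is narrow. Toxicity-related misses are DLTs, drop-outs are replaced, withdrawals may be replaced, and a delay shorter than about 14 days still puts dose 2 inside the window. All of this stands and limits the point to one kind of subject.

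There are also safeguards. Escalation is agreed in cohort-review calls (section 5.4.5). A lower MTD may be set from toxicities that appear after the window (section 5.4.2). A dose with only three treated subjects needs at least three more before Phase 2 (section 3.1.1.1). These reduce the lasting effect on the MTD. They are discretionary, or they act after the next cohort may already have been dosed, and any added subjects fall under the same definition.

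Half the doses is also not half the exposure. With the monkey half-lives in Table 1 (187 to 289 h), and assuming one-compartment decay and similar human kinetics, one dose gives about 56% to 59% of the two-dose 28-day AUC and 69% to 78% of the peak. Equal risk per dose is therefore only a working assumption, which is why a range is shown.

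A reader might draw three stronger conclusions that the documents do not support:
- That any half-dosed subject can count as DLT-free. Table 3 and the replacement rules close most routes.
- That a reduced second dose is an equal loophole. Table 4 attaches reduction to Grade 3 events, most non-hematologic Grade 3 events are already DLTs, and a modification in the window needs discussion with the medical monitor. What is left is small and driven by toxicity.
- That one such subject decides the escalation. At a 30% rate a one-dose subject hides a DLT with probability 0.300 − 0.163 = 0.137, so the outcome is unchanged about 86% of the time.

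**Conclusion.** The gap is real and narrow, and it should be closed. Read as written, section 9.2.1 counts as DLT-free a subject who stays on study but whose second dose is delayed past Day 28 for a logistical or unrelated medical reason. The resulting bias favours escalation and a Phase 1b verdict of safe.

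The size is modest: about 6 to 7 points on the chance of escalating if one of the first three subjects is affected, and about 1.4 to 5.7 points at a 30% DLT rate once an assumed 5% to 20% frequency is averaged in. Confidence is high on the wording and lower on the size, which rests on an assumed per-dose risk and an assumed frequency. The two-dose count applies to the 14-day schedule; alternate schedules may differ. It would go too far to infer that the MTD will be wrong: the point is that the definition permits an avoidable bias.

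**What to change.** Reconcile section 9.2.1, the synopsis, section 3.1.1.1 and section 3.3.2 around one definition, written for whichever schedule is in use:
- A subject without a DLT is evaluable only after receiving every dose planned for the 28-day window, at the assigned level, and completing 28 days of follow-up.
- A subject without a DLT who does not meet this is replaced for the escalation decision and kept in the safety analysis set.
- A subject with a DLT always counts, whatever number of doses was given.
- The same definition applies to the Phase 1b rule.

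Section 5.4.6 can keep its allowance for delays, with a cross-reference saying what such a delay does to evaluability. The maximum of 30 evaluable subjects does not change, because non-evaluable subjects are already replaced; only the number enrolled may rise. The cost is protocol wording, an occasional replacement subject and a short cohort delay when that happens.

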Phase 2 of the study will further evaluate the safety, tolerability, preliminary efficacy, PK, and pharmacologic activity of the RP2D of NC762 in subjects with advanced or metastatic non-small cell lung (squamous cell), hepatocellular carcinoma (HCC), HER2+ breast, and ovarian cancer. A fifth cohort may be included and will enroll patients of a tumor type pending outcomes of the Phase 1. A Simon 2-stage design will be utilized with a stopping rule to allow for early termination of a cohort at the end of Stage 1 if there are insufficient responses observed. During Stage 1, 12 evaluable subjects will be enrolled in each cohort; if no responses are observed within the cohort then the cohort will be discontinued. If at least 1 response is observed, 12 additional evaluable subjects will be enrolled in the cohort (Stage 2), for at least 24 evaluable subjects per cohort.

Subjects will continue to receive NC762 at the RP2D and schedule until protocol-defined withdrawal criteria are met. Continuous evaluation of toxicity events will be performed throughout enrollment in Phase 2 of the study. If the cumulative incidence of DLTs occurs in $\geq 33\%$ of subjects after 6 subjects have been observed for at least 28 days, further enrollment may be interrupted until the sponsor has determined the appropriate course of action. All AEs, regardless of the time of occurrence on study may be considered in determining the appropriate dose, schedule, and MNTD.

Toxicity will continue to be monitored throughout the treatment period. If $> 33\%$ of subjects (minimum of 6 subjects) experience a \geq Grade 3 toxicity related to study drug after completing ≥ 4 cycles, then the MNTD will be determined in conjunction with the investigators and sponsor based on all available safety data.

NC762 Study Schematic

TARGET SUBJECT POPULATION

Men and women, 18 years or older, with advanced solid malignancies who have progressed on standard treatment, who have been unable to tolerate standard therapy, who have refused standard therapy, or for whom no standard anticancer therapy exists may be enrolled. Subjects must provide written informed consent and have adequate organ function. Subjects must present with measurable disease based on RECIST v1.1 and consent to have a non-target lesion biopsied before and during treatment. Subjects with certain serious medical conditions (in addition to the diagnosis of cancer) would be excluded from participation in the trial.

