3.1.2 Phase 2 – Dose Expansion

Phase 2 of the study will further evaluate the safety, tolerability, preliminary efficacy, PK, and pharmacologic activity of the RP2D of NC762 in subjects with advanced or metastatic non-small cell lung (squamous cell), hepatocellular carcinoma, HER2+ breast, and ovarian cancer, or other tumor identified based upon emerging data. Each cohort will be comprised of an individual tumor type. Biopsies at pre-screening and on treatment will be required of all enrolled Phase 2 subjects. During Phase 2 Dose Expansion, subjects with CLIA validated B7-H4+ staining on the membrane of tumor cells confirmed by tumor biopsies will be considered eligible to enroll.

A Simon 2-stage design will be utilized with a stopping rule to allow for early termination of a particular cohort at the end of Stage 1 if there are insufficient responses observed. During Stage 1, 12 evaluable subjects will be enrolled in each cohort; if no responses are observed within the cohort then the cohort will be discontinued. If at least 1 response is observed, 12 additional evaluable subjects will be enrolled in the cohort (Stage 2), for at least 24 evaluable subjects per cohort.

Subjects will continue to receive NC762 at the RP2D and schedule until protocol-defined withdrawal criteria are met. Continuous evaluation of toxicity events will be performed throughout enrollment in Phase 2 of the study. If the cumulative incidence of DLTs occurs in $\geq 33\%$ of subjects after 6 subjects have been observed for at least 28 days, further enrollment may be interrupted until the sponsor has determined the appropriate course of action. All AEs, regardless of the time of occurrence on study may be considered in determining the appropriate dose, schedule, and MNTD.

Toxicity will continue to be monitored throughout the treatment period. If > 33% of subjects (minimum of 6 subjects) experience a \geq Grade 3 toxicity related to study drug after completing \geq 4 cycles, then the MNTD will be determined in conjunction with the investigators and sponsor based on all available safety data.

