3.3 Number of Subjects

3.3.1 Planned Number of Subjects

Up to approximately 170 evaluable subjects may be enrolled in this study.

- Phase 1a Dose Escalation – Approximately 15–30 evaluable subjects
- Phase 1b Safety Expansion – Approximately 20 additional evaluable subjects
- Phase 2 Dose Expansion – Up to 120 evaluable subjects (up to 60 in stage 1)

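### Does it matter that the Phase 2 Simon stages are counted on evaluable subjects in 3.1.2 but on subjects in 9.2.2?

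*Combined protocol and SAP*

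**What the plan says.** Section 9.2.2 sets a Simon two-stage rule for each tumor type, with 5% as the uninteresting response rate. On Stage 1 it says: "During Stage 1, 12 subjects will be enrolled; if no responses are observed, then the cohort will be discontinued". Otherwise, "then 12 additional subjects will be enrolled (Stage 2), for a maximum of 24 subjects per tumor type in Phase 2". The design inputs follow: "The detailed calculation is based on a 1-sided Type I error of 0.05 and power of 80% to detect a 25% response rate".

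The synopsis and section 3.1.2 describe the same rule with another noun and another bound: "12 evaluable subjects will be enrolled in each cohort" in Stage 1, and after Stage 2 "for at least 24 evaluable subjects per cohort". Section 3.3.1 gives the Phase 2 total as "Up to 120 evaluable subjects (up to 60 in stage 1". Section 9.2 opens with "A maximum of 170 eligible subjects in Phase 1 and Phase 2 (50 + 120) will be included in this study".

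Evaluability is defined in 9.2.1 for toxicity only: "Subjects evaluable for DLTs are defined as the subjects who take a full dose of NC762 and then are followed up for 28 days". Section 9.1 has no response-evaluable set. It assigns everything except safety and PK to the full analysis set (FAS), which requires one full dose and no scan. For Phase 2, section 3.3.2 mentions only unmet biopsy requirements and ineligibility. Section 9.3 plans no formal hypothesis test, and section 9 leaves further analysis detail to a separate SAP.

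**The concern.** A floor of 24 evaluable subjects and a ceiling of 24 subjects agree only when exactly 24 are counted and all of them are evaluable. The first scheduled scan is at Week 8, so a subject who leaves earlier may have no response assessment.

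Suppose 12 are dosed, 2 have no post-baseline scan and none responds. Read literally, 9.2.2 closes the cohort. Under 3.1.2, if those 2 are not evaluable, 2 more are dosed before the decision. The Stage 1 stop is the only efficacy decision rule the readable text states for a cohort.

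Replacing early leavers, who are all non-responders, also raises the response rate among those counted. An inactive drug would then pass more easily, and the response rate reported on the FAS would use a larger denominator than the decision did.

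**Working it through.** **Inputs.** From 9.2.2: null rate 5%, target rate 25%, one-sided type I error 0.05, power 80%, stop at 0 of 12, total 24. The readable text gives no final boundary c, so it is derived. The share d of dosed subjects without a response assessment is not in the documents; it is assumed and a range is shown.

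**1. The design itself.** With X1 and X2 independent Bin(12, p),

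P(pass) = Σ over x ≥ 1 of P(X1 = x) · P(X2 ≥ c − x).

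For c = 4:

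- p = 0.05: 0.3413 × 0.0196 + 0.0988 × 0.1184 + 0.0173 × 0.4596 + 0.0022 = 0.0286
- p = 0.25: 0.1267 × 0.6093 + 0.2323 × 0.8416 + 0.2581 × 0.9683 + 0.3512 = 0.874

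| Boundary | Type I error | Power |
|---|---|---|
| 3 or more of 24 | 0.105 | 0.941 |
| 4 or more of 24 | 0.029 | 0.874 |
| 5 or more of 24 | 0.006 | 0.748 |

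Only 4 of 24 meets both stated limits. The chance of stopping at Stage 1 is 0.95^12 = 54.0% at a 5% rate and 0.75^12 = 3.2% at 25%. The 24 is not the smallest sample that would do (the minimax Simon design for these inputs needs 16), but it satisfies them.

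**2. Which count is meant.** Section 3.3.1's 120 evaluable is 5 × 24, and its 60 in Stage 1 is 5 × 12, for the four named cohorts plus the possible fifth. In 9.2, the 50 in 50 + 120 is 30 DLT-evaluable plus 20 Phase 1b subjects. Section 9.2.1 describes those Phase 1b subjects as evaluable and then, within the same sentence, simply as subjects; 3.3.1 calls them evaluable. So section 9.2 uses the shorter word for evaluable people, and 9.2.2 never says all or dosed.

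**3. If the 5% and 25% refer to dosed subjects and unassessed subjects are replaced.** The counted null rate becomes 0.05/(1 − d).

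| d | Counted rate | Pass Stage 1 | Type I error, 4 of 24 |
|---|---|---|---|
| 0 | 0.0500 | 46.0% | 0.029 |
| 10% | 0.0556 | 49.6% | 0.040 |
| 20% | 0.0625 | 53.9% | 0.057 |
| 30% | 0.0714 | 58.9% | 0.085 |

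The error reaches 0.05 at a counted rate of 0.0598, so d = 1 − 0.05/0.0598 = 16.4%.

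**4. If the rates refer to evaluable subjects and all dosed subjects are counted,** with unassessed ones as non-responders, the rates become 0.05(1 − d) and 0.25(1 − d).

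| d | Type I error | Power |
|---|---|---|
| 0 | 0.029 | 0.874 |
| 10% | 0.020 | 0.809 |
| 20% | 0.014 | 0.722 |
| 30% | 0.009 | 0.612 |

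Power falls below 80% once d exceeds about 11%.

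**5. A cohort that overruns 24.** With rates on evaluable subjects and the boundary held at 4, the type I error is 0.0453 at 28, just under 0.0500 at 29 and 0.0549 at 30. A cohort would have to overrun by six to break the limit.

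**6. The worked example.** The two sections give stop and defer, not stop and continue. Two extra subjects at a 5% rate yield a response with probability 1 − 0.95² = 9.75%, so in about nine cases in ten the cohort closes anyway.

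**The case for a change.** The best case for a change is that a floor and a ceiling cannot both be the rule, and that counting on the wrong set can break one of the stated limits in either direction: type I error above d = 16.4%, or power above about 11%. In a refractory population some subjects will be lost before Week 8, and nothing supplied says whether they count.

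The wording difference and the missing definition stand. The rest is weaker.

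The two breaches need opposite assumptions about which population the 5% and 25% describe, and the documents do not say. Counting all dosed subjects therefore cannot be called the option that protects the error rates. It protects type I error and may cost power. Replacing unassessed subjects does the reverse, and needs 24/(1 − d) dosed, or 26.7 to 34.3 per completed cohort for d from 10% to 30%.

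A large d is also not obvious. Table 7 (footnote r) and section 7.6.1.1.3 ask for a scan at discontinuation in subjects who stop without confirmed progression, unless one was done in the preceding 4 weeks, and for continued imaging in those who stop for other reasons. Section 7.6.1.1.2 allows earlier imaging when clinically indicated. Deaths and withdrawn consent would still leave gaps.

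**Conclusion.** No change to the plan follows. Read with 3.3.1, the sections point to 24 evaluable subjects per cohort, and the floor-versus-ceiling wording is a drafting slip. The stop at 0 of 12 can be run as written. The final boundary is not stated in the readable text, but the inputs fix it at 4 of 24 (type I error 0.029, power 0.874).

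The response rate is reported on the FAS with an exact 95% interval, so any gap between the decision count and the reported denominator will be visible: at d = 20%, 4/24 = 16.7% against 4/30 = 13.3%. Efficacy is secondary, 9.2.2 describes the cohort size as guided by the Simon design, and no test is planned that a nominal 0.029 or 0.057 would control.

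Defining who counts as response-evaluable is detail that the analysts can settle in the SAP before the first Stage 1 decision. The choice between counting dosed and counting evaluable subjects is a fair trade-off.

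This rests on reading subjects in 9.2.2 as shorthand for evaluable subjects, on the derived boundary of 4, and on d being unknown. Figure 1 and the separate SAP were not available and may already settle the definition or the boundary.

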9 STATISTICS

Tabular summaries will be presented by dose groups. Categorical data will be summarized by the number and percentage of subjects in each category. Continuous variables will be summarized by descriptive statistics including mean, standard deviation, median, minimal, and maximal values. All analyses, unless specified otherwise, will be based on as-treated population, which includes all subjects who receive any dose of NC762. Additional details of statistical analyses will be described in the Statistical Analysis Plan (SAP).

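### Does the Phase 2 Simon design in section 9.2.2 need a printed final cut-off and one cohort size before its stated error rates can stand?

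*Combined protocol and SAP*

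**What the plan says.** Section 9.2.2 takes 5% as the response rate of no clinical interest in every tumor type and 25% as the rate to detect. It says "The sample size for each tumor type will be guided by the Simon 2-stage design" and then "The detailed calculation is based on a 1-sided Type I error of 0.05 and power of 80% to detect a 25% response rate". Twelve subjects enter Stage 1. A cohort with no response stops; otherwise 12 more enter, "for a maximum of 24 subjects per tumor type in Phase 2".

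The synopsis and section 3.1.2 give the same 12 + 12 and the same Stage 1 stop, but end differently: "12 additional evaluable subjects will be enrolled in the cohort (Stage 2), for at least 24 evaluable subjects per cohort".

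On totals, section 9.2 says "A maximum of 170 eligible subjects in Phase 1 and Phase 2 (50 + 120) will be included in this study". Section 3.3.1 allows up to 120 evaluable subjects in Phase 2, of whom up to 60 are in Stage 1.

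On analysis, section 9.3 plans no formal hypothesis test, and section 9.5.3 reports the objective response rate, a secondary endpoint, with a 95% exact confidence interval. Section 9 leaves further detail to a separate SAP. The legend of Figure 1 in section 3.1 reads "RR: Response Rate (ORR) per RECIST v1.1"; the figure itself is not shown in the available copy, and nor is the synopsis schematic.

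**The concern.** Type I error and power belong to a complete decision rule. The visible text gives the Stage 1 half of the rule but not the number of responses that makes a 24-subject cohort a success, so the 0.05 and 80% cannot be checked from the text alone.

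Guessing the cut-off also looks risky. The smallest Simon design for these inputs has the same first stage (12 subjects, stop at 0) but ends at 16 subjects with success at 3 or more. Carried over to 24 subjects, a cut-off of 3 would give about twice the permitted type I error. A cohort ending with exactly 3 of 24 would then be read in two ways.

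The floor and the cap on cohort size add to this, because the cut-off that meets the limits depends on the total. If cohorts could run past 24, the rule would shift with them.

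**Working it through.** **Inputs, all from section 9.2.2.** Uninteresting rate 5%; target rate 25%; one-sided type I error 0.05; power 80%; first stage of 12 with a stop at 0 responses; second stage of 12.

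**Formula.** Success with cut-off k requires at least one response in the first 12 and at least k in all 24. With response rate p,

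P(success) = P(X₂₄ ≥ k) − (1 − p)¹² × P(X₁₂ ≥ k),

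where X₂₄ and X₁₂ are binomial with 24 and 12 subjects. The subtracted term removes the paths that Stage 1 has already stopped. The stop probability is 0.95¹² = 0.5404 at 5% and 0.75¹² = 0.0317 at 25%.

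**Printed design, 12 + 12.**

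| Cut-off | Type I error (p = 5%) | Power (p = 25%) | Limits met |
|---|---|---|---|
| ≥3/24 | 0.1159 − 0.5404 × 0.0196 = 0.105 | 0.9602 − 0.0317 × 0.6093 = 0.941 | power only |
| ≥4/24 | 0.0298 − 0.5404 × 0.0022 = 0.029 | 0.8850 − 0.0317 × 0.3512 = 0.874 | both |
| ≥5/24 | 0.0060 − 0.5404 × 0.0002 = 0.006 | 0.7534 − 0.0317 × 0.1576 = 0.748 | error only |

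The printed sizes are therefore compatible with the printed limits, and with one cut-off only.

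**Comparison with the standard Simon designs.** A search over designs meeting 0.05 and 80% gives:

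- smallest total: 12 then 16 subjects, stop at 0, success at ≥3 (0.043 / 0.801; expected size at 5% of 13.8);
- smallest expected size: 9 then 17 subjects, stop at 0, success at ≥3 (0.047 / 0.812; expected size 12.0).

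The plan's expected size at 5% is 12 + 12 × (1 − 0.540) = 17.5. It is larger than either, but section 9.2.2 claims only to be guided by the method. The extra subjects buy power of 0.874 and a narrower interval.

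**How often 3 of 24 would occur.** From the table, 0.1054 − 0.0286 = 0.077 at a true rate of 5%, and 0.9409 − 0.8739 = 0.067 at 25%.

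**What the planned analysis gives.** The two-sided 95% exact interval at 4/24 runs from 4.7% to 37.4%; at 5/24 its lower limit is 7.1%.

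**Cohort size.** 12 + 12 = 24 in all three places. With the optional fifth cohort, 5 × 24 = 120 and 5 × 12 = 60, which are the totals in section 3.3.1; 50 + 120 = 170 is the total in section 9.2. A floor of 24 and a cap of 24 agree only at 24.

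**The case for a change.** The best case for a change is that a protocol that justifies its size by type I error and power should print the rule that attains them, above all in an open-label study where investigators assess response. The planned interval does not supply that rule. If success were read as the interval lying above 5%, 5 of 24 would be needed, and power would be 0.748, below the stated 80%. The cut-off also depends on the total. At 26 subjects both 4 (0.037 / 0.905) and 5 (0.008 / 0.808) qualify; at 30, a cut-off of 4 exceeds the error limit (0.055) and 5 is needed (0.015 / 0.887).

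The arithmetic stands, and so does the mismatch in wording. The conclusion does not follow. The visible plan declares no cohort a success or failure at 24; the one Phase 2 efficacy rule it operates is the stop at 0 of 12, which is fully specified. Nothing in the plan suggests a cut-off of 3, so the two readings of a 3/24 cohort come from outside it. Adding a threshold of 4 would also carry a cost. It would put a success rule into a plan that disclaims testing, and a cohort could meet it while its planned interval, 4.7% to 37.4%, still includes the uninteresting rate. As for totals of 26 or 30 in every cohort, the cap in section 9.2.2 and the overall 120 rule them out.

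**Conclusion.** No change is needed. No printed figure is wrong: 12 + 12 with the stop at 0 of 12 can meet 0.05 and 80%, with attained values of 0.029 and 0.874 at a cut-off of 4. The missing cut-off is a gap in detail that alters no planned result, because the response rate is a secondary endpoint reported as an estimate with an exact interval. Type I error and power serve here as sizing guidance, and an analyst who wants a benchmark can derive the only one that fits. The floor-against-cap wording is a real but near-clerical slip that the plan's own sums resolve at 24; tidying it would change no cohort, total or analysis.

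This rests on three assumptions: a cohort that continues has exactly 24 evaluable subjects, section 9.3 means what it says about testing, and neither the unseen figure nor the separate SAP sets a conflicting cut-off. If a later document used a formal success rule per cohort, the cut-off and its exact error rates would need to be stated there.
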